The exact mechanism of resistance to copanlisib in various lymphomas and solid tumors remain poorly understood. As described above, we have reported that PI3K inhibitors can induce hyperinsulinemia, which in turn leads to activated survival pathway in cancer cells[79]. Our preliminary results demonstrate that in mice copanlisib stimulated the blood level of insulin, which is effectively mitigated by the ketogenic diet. Importantly, the ketogenic diet markedly improves the survival of KPC mice treated with copanlisib (BAY 80-6946).

Collectively, the results presented above suggest that copanlisib may have encouraging clinical activity in indolent B-cell NHL such as FL and MZL, aggressive lymphomas such as PTCL and DLBCL, and solid tumors such as endometrial cancer. Furthermore, ketogenic diet may mitigate hyperinsulinemia associated with copanlisib in many patients, leading to improved treatment response to copanlisib and prolonged patient survival.

Fasting requirements and pre-dose glucose levels

Period	Fasting ≥ 8 hrequiredbeforefirstglucosemeasurement	Pre-dose glucose levels (first glucose measurement)
Day 1 Cycle 1	Yes	≤ 125 mg/dL (non-diabetic patients)
		<160 mg/dL (diabetic patients)
Subsequent Infusion after Day 1 Cycle 1	No ^a	<160 mg/dL (fasting) < 200 mg/dL (non-fasting)

^aThe decision regarding meal timing and fasting can be made by the investigator based on glucose response patterns during prior treatment days

The investigator will accurately document fasting/non-fasting for each glucose measurement done at the site.

• Fasting refers to no caloric intake for ≥ 8 h.

• Non-fasting status includes any caloric intake such as meals and also juice, snacks, and other caloric intake not consistently called a meal.

From Cycle 1 Day 1 onwards, glucose measurements at the site may be done either by laboratory analysis or in capillary blood using a hand-held glucose meter. If hand-held capillary glucose meters are chosen, the appropriate calibration of glucose meters will be documented. Any capillary or plasma glucose of > 250 mg/dL should be confirmed by repeated laboratory analysis.

Laboratory criteria for dosing of copanlisib

Blood glucose must be performed and assessed on the day of infusion. Glucose lowering medication can be used to optimize pre-infusion glucoses.

Laboratory tests must be performed and assessed prior to each infusion of copanlisib. The results can be done +/- 2 days.

Laboratory Test	Criteria

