Glucose	< 160 mg/dL (fasting) or < 200 mg/dL (non-fasting)
Hemoglobin	$\geq 8 \text{ g/dL}^{a}$
ANC	$\geq 1,000/mm^3$
Platelets	\geq 75,000/mm ^{3 b}
ALT	<2.5 x ULN °
AST	<2.5 x ULN ^d
Total bilirubin	within normal limits ^e
GFR (MDRD)	\geq 35 mL/min/1.73 m ²

Laboratory criteria for day 1 of each cycle

ALT = Alanine aminotransferase; ANC = Absolute neutrophil count; AST = Aspartate aminotransferase; GFR = Glomerular filtration rate; MDRD = Modification of Diet in Renal Disease; ULN = Upper limit of normal.

^{a:} If hemoglobin is < 8 g/dL but $\ge 6 \text{ g/dL}$ on the day of planned study drug administration it is permissible to give the study drug dose as scheduled and transfuse within 48 hours after the dose, if the patient is hemodynamically stable and in opinion of investigator benefits outweigh risks. Rationale and treatment should be recorded in source document and Electronic case report form (eCRF).

^{b:} For patients with lymphomatous bone marrow infiltration at study entry (local assessment), platelet count \geq 50,000/mm3. This value should be used throughout the study irrespective of bone marrow status changes. Platelet transfusion should not be given less than 7 days before the exam collection.

c < 5 x ULN in patients with documented liver involvement by lymphoma or with biliary obstruction due to lymphoma.

 $\frac{d}{d} < 5$ x ULN in patients with documented liver involvement by lymphoma or with biliary obstruction due to lymphoma.

 e^{i} < 3 x ULN in patients with Gilbert-Meulengracht syndrome, patients with cholestasis due to compressive adenopathies of the hepatic hilum or documented liver involvement by lymphoma.

On Days 8 and 15 of each cycle, the dose of copanlisib will be administered only if, on the day of scheduled dosing, the following laboratory test criteria are met (blood tests from the previous day is acceptable):

- ANC ≥ 500/mm³ (and G-CSF/GM-CSF is mandatory if ANC<1000/mm³ and should be administered as per label)
- Hemoglobin ≥ 8 g/Dl (Transfusion is allowed)
- Platelet \geq 75,000/mm³ (Transfusion is allowed)

Doses of copanlisib may be delayed by up to 2 days. The minimal time between each infusion of copanlisib is 5 days.

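### Two tables set different pre-dose glucose limits for non-diabetic patients at the first copanlisib infusion, and the available text does not say which governs

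*Combined protocol and SAP*

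**What the plan says.** Both rules are in the combined protocol and SAP, in consecutive parts of the synopsis.

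- **Fasting requirements and pre-dose glucose levels.** The row for Day 1 of Cycle 1 requires a fast before the first glucose measurement. The limits are "≤ 125 mg/dL (non-diabetic patients" and "<160 mg/dL (diabetic patients". A separate row, "Subsequent Infusion after Day 1 Cycle 1", drops the fasting requirement and sets below 160 mg/dL fasting or below 200 mg/dL non-fasting. Fasting is defined once: "Fasting refers to no caloric intake for ≥ 8 h".
- **Laboratory criteria for dosing of copanlisib.** The lead-in states "Blood glucose must be performed and assessed on the day of infusion" and "Laboratory tests must be performed and assessed prior to each infusion of copanlisib". The table that follows is captioned "Laboratory criteria for day 1 of each cycle". Its glucose row reads "< 160 mg/dL (fasting) or < 200 mg/dL (non-fasting". It does not separate diabetic from non-diabetic patients, and it does not mention Cycle 1 or the fasting table.

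**The concern.** The first cycle is one of the cycles that the dosing table's caption covers, and the first infusion is one of the infusions that its lead-in covers. Read as written, both tables apply to the same reading on the same morning, and for some non-diabetic patients they give different answers.

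This is the check before the first dose of a drug whose effect on insulin is central to the trial's rationale. The dosing table lists all the day 1 laboratory tests together, glucose included, so staff could reasonably use it as their checklist. A site that did so would clear some patients for a first dose whom the fasting table does not clear. Several institutions take part, so practice could differ between them. The protocol also allows glucose-lowering medication before infusion, and the value to aim for at this visit depends on which table is read.

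**Working it through.** There is no sample size, power or error rate to reproduce. The check sets the two rules side by side for Cycle 1 Day 1, with G the pre-dose glucose in mg/dL.

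**Inputs**

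- Rule A (fasting table, Day 1 of Cycle 1): fasted for at least 8 h, and G ≤ 125 if non-diabetic or G < 160 if diabetic.
- Rule B (dosing table, day 1 of any cycle): G < 160 if fasting, G < 200 if not.
- Glucose is tested on the infusion day, so A and B are applied to the same reading.
- The caption follows its table in the text, as the caption of the inclusion laboratory table also does. Assigning it to the dosing table is therefore sound.

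**Comparison**

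| Patient and state | Rule A met | Rule B met | Where they differ |
|---|---|---|---|
| Non-diabetic, fasting | G ≤ 125 | G < 160 | 125 < G < 160 |
| Diabetic, fasting | G < 160 | G < 160 | nowhere |
| Either group, non-fasting | not met (no fast) | G < 200 | B lists a limit; A requires a fast |

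**Size of the overlap.** In whole mg/dL, the non-diabetic fasting range runs from 126 to 159, which is 159 − 126 + 1 = 34 values. Each meets B and fails A. At 140 mg/dL, for example, 140 < 160 satisfies B and 140 > 125 fails A.

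**Direction.** No reading meets A and fails B: among fasting patients A's limit is either lower (125 against 160) or the same (160 against 160), and a non-fasting patient never meets A. Rule A is therefore at least as strict throughout.

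**Later infusions.** The fasting table's row for later infusions and the dosing table carry the same limits, so they do not differ after Cycle 1 Day 1.

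**Can patients arrive in the disputed range?** The inclusion laboratory table uses the same glucose limits as Rule B. A non-diabetic patient with a fasting value of 140 mg/dL therefore meets the glucose entry criterion and can go on to the diet run-in. If the value is similar on Day 1, the two tables disagree. The run-in may lower it, but the documents do not say by how much.

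**The case against.** The strongest reply is that these are a specific rule and a general one, and that both can be met. The fasting table has a row for Cycle 1 Day 1 alone, and the dosing table repeats the limits of the other row, for later infusions. A reader meets the dedicated row first, and a site that applies both tables ends up following it. The dosing table does not say that meeting its criteria is sufficient. Other glucose controls exist as well: the diabetes and HbA1c exclusions, the run-in diet and same-day testing.

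Much of this stands. The specific-over-general reading is plausible and the instructions are not impossible to follow. But the reading has to be supplied by the site, because the available text does not state it and the caption takes in every cycle.

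Three stronger readings are tempting, and the documents do not support them.

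- *That the protocol orders a patient both dosed and held.* Neither table states what happens when a criterion fails. Holding the dose is an inference.
- *That every non-fasting patient below 200 mg/dL is a second group in direct conflict.* The dosing table gives a limit for a non-fasting reading but does not waive the fast. This is a mismatch in scope, not a second numeric contradiction.
- *That glucose and insulin data would be a mix of fasting and non-fasting values because of this wording.* The investigator must record fasting status for each glucose measurement made at the site. Fasting is by design not required after the first infusion, and neither table sets an insulin criterion. These markers are exploratory.

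**Conclusion.** The inconsistency is real and narrow. It is confined to Cycle 1 Day 1, and its firm numeric part is non-diabetic patients with a fasting glucose above 125 and below 160 mg/dL. A secondary mismatch is the non-fasting limit listed for a visit that requires a fast. The scope of the dosing table is wrong or incomplete for one visit; the trial's design and its response-rate analysis are not in question.

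The conclusion assumes that the caption belongs to the dosing table and that failing a pre-dose criterion is meant to affect dosing. It is also limited to the text available: Sections 5.6 and 6.6 are cited but are not in the public document, so a precedence statement there cannot be excluded. The documents give no glucose distribution, so the number of patients affected is unknown and could be none.

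**What to change.** Reconcile the two tables so that a single glucose and fasting rule applies to Cycle 1 Day 1. Then either limit the dosing table's glucose row to the visits it is meant for or add a cross-reference to the fasting table. If Section 5.6 or 6.6 already states which table governs, repeat that next to the dosing table. Which limit applies at the first infusion is the sponsor's clinical decision, and no view is offered here.

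The cost is protocol wording, with the same correction carried into any site dosing checklist built from these tables. Sample size, visits and analyses do not change.
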